Taken together, these results suggest that the A β burden required to elicit an MCI profile could vary across patients. Some may be susceptible to minimal levels of A β deposition, showing clinical symptoms at earlier stages of A β cerebral pathology, while others would only show clinical symptoms after prolonged A β deposition.

Furthermore, we hypothesized that in those a-MCI and vm-AD patients deemed as A β -negative, the clinical symptomatology may be primarily driven by soluble A β isoforms and/or perivascular deposits of A β 40, not detectable by current A β neuroimaging, and nevertheless susceptible to being modified by our anti-A β 40 treatment. We assume that by making amyloid eligibility more liberal, there may be some loss in specificity; however, this loss may be worth the gains made by treating a less progressed population. In conclusion, we think that treatment with ABvac40 may benefit a-MCI and vm-AD patients, regardless of their amyloid-PET status as determined by the currently validated thresholds.

Nevertheless, it is well known that on average the progression to dementia in amyloid-PET negative MCI or vm-AD patients is less probable and significantly slower than in their counterparts with demonstrated amyloid burden, and this is why we decided to use this biomarker to stratify (not to select or to reject) the subjects for the assessment of the secondary exploratory efficacy objectives [28-30].

Thus, in line with the EMA/CHMP/539931/2014 document (Draft guideline on the clinical investigation of medicines for the treatment of Alzheimer's disease and other dementias), the present ABvac40 phase II clinical trial will be carried out on a-MCI and/or vm-AD patients, characterized by their amyloid-PET neuroimaging profile as either A β -positives or A β -negatives. Eligible subjects must meet clinical criteria for either a-MCI as defined by the National Institute on Aging-Alzheimer's Association [31]; or vm-AD as defined by National Institute of Neurological and Communicative Diseases and Stroke/Alzheimer's Disease and Related Disorders Association (NINCDS-ADRDA) (see section 2, pag 29).

Patients will be recruited regardless their amyloid-PET state (positive or negative), which will be assessed as per the currently validated visual reading for flutemetamol. The amyloid-PET positive and amyloid-PET negative patients will be independently randomized following the same verum:placebo ratio of 1:1 [Part A].

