Mixed-model repeated-measures (MMRM) analyses will be performed for all the primary and secondary efficacy variables (section 7.1) to assess between-group differences in change scores from baseline (V0/V1) to Int-6m (V16), V21 and to the final visit (V25). The dependent variable in each MMRM analysis will be “change from baseline”. Fixed effects will include baseline scores on outcome measures, age at baseline, group assignment, amyloid positivity, study visit, and treatment-by-visit interaction. Additionally, covariates that are significantly associated with the response measure ($p < 0.15$) and are out of balance at baseline ($p < 0.2$) will be included as fixed effects. Variables considered as potential covariates in each model will be demographic variables, baseline characteristics, general treatment for AD and concomitant medication.

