1.1 Purpose and Scope of Analysis Plan

The purpose of this statistical analysis plan (SAP) is to provide detailed information to aid in the implementation of the statistical analysis of the study data. It briefly summarizes the protocol, describes the analysis sets that will be analyzed, and describes the analyses to be performed. The details of the specific statistical methods that will be used are provided. Post database lock (DBL), it may become apparent that the planned analyses should be modified, e.g., modeling assumptions are untenable. Any modification to the original analysis plan will be identified and described in the clinical study report (CSR).

Table, figure, and listing specifications are in separate documents. This analysis plan is meant to supplement the study protocol. If differences occur between analyses described in the SAP and the current protocol, those found in this SAP will assume primacy.

This SAP is written with due consideration of the recommendations outlined in the most recent International Conference on Harmonisation (ICH) E9 Guideline entitled Guidance for Industry: Statistical Principles for Clinical Trials and the most recent ICH E3 Guideline, entitled Guidance for Industry: Structure and Content of Clinical Study Reports and will be finalized prior to DBL.

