6.1.2 Sensitivity Analyses for Primary Outcome

No adjustments will be made for multiple testing of study parameters. Therefore, interpretation of p-values for these sensitivity analyses should be considered descriptive in nature.

The following analyses will be performed for the primary outcome:

1. The primary analyses will be repeated for the PP Analysis Set.
2. The primary analysis (t-test) will be repeated, using the mITT Analysis Set to test the hypothesis:
 - Null hypothesis: average $M\Delta$ anti- $A\beta$ 40 (ABvac40) - average $M\Delta$ anti- $A\beta$ 40 (placebo) ≤ 1.778
 - Alternative hypothesis: average $M\Delta$ anti- $A\beta$ 40 (ABvac40) - average $M\Delta$ anti- $A\beta$ 40 (placebo) > 1.778
3. The change in anti- $A\beta$ 40 antibody signal from baseline to each post-baseline efficacy visit will be analyzed using a Mixed-Model Repeated Measures (MMRM), using the mITT Analysis Set.

The MMRM will include change from baseline in anti- $A\beta$ 40 antibody signal as the dependent variable; treatment, protocol-specified visits, treatment-by-visit interaction, and amyloid positivity as the fixed effects; baseline anti- $A\beta$ 40 antibody signal and baseline age as covariates; and measures within-patient at each visit as a repeated measure. The variance-covariance matrix will be assumed to be unstructured. If the procedure does not converge then a compound symmetric variance-covariance matrix will be used instead.

The least squares (LS) mean change from baseline will be presented for each treatment group (ABvac40 and placebo) for each post-baseline scheduled visit, along with the LS mean treatment difference (ABvac40 – placebo), 95% CI for mean treatment difference and p-value for comparison of treatment groups.

The following is sample SAS® code for the MMRM:

```
proc mixed data=pp method=ml;
  class Patient Treatment Visit a_PET;
  model change = Baseline a_PET Treatment Visit age
    Treatment*Visit / s;
  repeated Visit / type=un subject=Patient r;
  lsmeans Treatment*Visit / pdiff cl;
run;
```

A plot of LS means over time will be presented by treatment group.

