6.1.3 Analysis of Secondary Outcome Variables

No adjustments will be made for multiple testing of study parameters. Therefore, interpretation of p-values for the analyses of secondary outcomes should be considered descriptive in nature.

The following analyses will be performed for all secondary outcomes specified in section 4.2.2 of this SAP (above), using the ITT Analysis Set:

1. The MMRM analysis described in section 6.2 will be repeated for all continuous parameters.

With the exception of levels of anti-A β 40 antibodies in CSF and plasma, the dependent variable will be the change from baseline in secondary outcome as the dependent variable; treatment, protocol-specified visits, treatment-by-visit interaction, and amyloid positivity as the fixed effects; baseline secondary outcome and baseline age as covariates; and measures within-patient at each visit as a repeated measure.

For the analysis of levels of anti-A β 40 antibodies in CSF and plasma, the dependent variable with the be recorded outcome value (i.e. not the change from baseline) and the baseline outcome covariate will be removed from the model.

The following factors may also be included in the model: ApoE carrier status, baseline use of AD symptomatic medication and clinical subgroup – MCI or vmAD, if found to be significantly associated with the response measure ($p < 0.15$).

2. A plot of LS mean change over time will be presented by treatment group.

All analysis will be repeated for baseline a-PET positive and baseline a-PET negative patients separately for the following parameters:

1. Disease biomarkers – all parameters listed in section 4.2.2.2 above.
2. Cognition assessment – MMSE, CDR-SB, RBANS, ADCS-ADL MCI, C-SSRS, IGE, EQ-5D-5L and TMT.

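### The pooled secondary MMRMs hold the baseline-score and amyloid effects constant over visits, so late-visit standard errors can be modestly too wide, and the estimate can be biased if the amyloid mix of dropouts differs by arm

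*Protocol*

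**What the plan says.** Protocol 9.1.2.2 sets the MMRM for change from baseline: "Fixed effects will include baseline scores on outcome measures, age at baseline, group assignment, amyloid positivity, study visit, and treatment-by-visit interaction". Treatment is the only term crossed with visit.

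SAP 6.1.2 uses the same terms for the antibody signal: "treatment, protocol-specified visits, treatment-by-visit interaction, and amyloid positivity as the fixed effects". Its sample code reads "model change = Baseline a_PET Treatment Visit age", followed by the treatment-by-visit product. It is fitted by maximum likelihood ("proc mixed data=pp method=ml") with an unstructured covariance ("repeated Visit / type=un subject=Patient r").

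SAP 6.1.3 applies this model to all continuous secondary outcomes. Its cross-reference says section 6.2, but the MMRM is in 6.1.2. For most outcomes it keeps "baseline secondary outcome and baseline age as covariates; and measures within-patient at each visit as a repeated measure". The same section repeats the disease-biomarker and cognition analyses separately in a-PET positive and a-PET negative patients, and calls the secondary p-values descriptive.

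SAP 1.1 says that where SAP and protocol analyses differ, "those found in this SAP will assume primacy". Here they agree, so neither corrects the other.

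Protocol 2.7 gives the reason for stratifying on a-PET: on average, "the progression to dementia in amyloid-PET negative MCI or vm-AD patients is less probable and significantly slower than in their counterparts".

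**The concern.** If the two amyloid groups progress at different speeds, the difference between them in change from baseline should be larger at month 24 than at month 6. A single a-PET coefficient cannot follow that. The part it misses goes into the late-visit residual, where a disease-modifying effect would be looked for. The same holds for baseline score if its relation to change strengthens over time.

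Two things are at stake in the overall-population models for cognition, PET, CSF and MRI. One is the width of the late-visit intervals. The other is whether the treatment difference is protected against dropout that is unbalanced on amyloid status. These data are meant to inform the Phase III go/no-go decision (Protocol section 2), and month-24 data will be thin: about 40% dropout is expected, and Part A may end at V23.

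**Working it through.** **Plan's own figures.** The documents give no standard error, power or N for any MMRM. The completer count reproduces: 120 × 0.6 = 72, against the stated 70 or so.

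**Inputs from the documents.** 120 patients, randomised 1:1 within a-PET strata (Protocol 4.3.2); about 50% amyloid-negative (Protocol 2.7); about 40% dropout (Protocol 9.2); unstructured covariance and ML (SAP 6.1.2). Post-baseline Part A visits: V16, V21, V23 and V25 for most cognitive scales; V21 and V25 for PET and CSF; V16, V21 and V25 for MRI volumetry.

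**Assumptions, not in the documents.** Residual SD 0.60, 0.75, 0.88 and 1.00 at months 6, 12, 18 and 24; correlation 0.75 to the power of the lag; amyloid gap and baseline slope growing linearly to the month-24 values below; no treatment effect. 1,200 simulated trials per scenario; Monte Carlo error of each mean about 0.006 SD.

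**Models compared at visit t.**
- Planned: α_t + τ_t·treatment + β·baseline + γ·aPET + δ·age.
- With interactions: the same, with β and γ replaced by β_t and γ_t.

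If the true effect is γ_t, the planned residual at visit t keeps (γ_t − γ)·aPET.

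**Precision at month 24, ML, about 40% dropout alike in both arms.**

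| Amyloid gap (SD) | Baseline slope (SD per SD) | SE planned | SE with interactions | SE excess, ML | SE excess, REML |
|---|---|---|---|---|---|
| 0 | 0 | 0.214 | 0.213 | none | −0.6% |
| 0.5 | 0 | 0.217 | 0.213 | 1.9% | 0.8% |
| 1.0 | 0 | 0.226 | 0.213 | 6% | 5% |
| 0.5 | 0.3 | 0.221 | 0.213 | 4% | 3% |
| 1.0 | 0.5 | 0.238 | 0.213 | 11.5% | 10% |

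A second simulation (1,800 trials per scenario, 60 per arm, 35–41% missing at V25, dropout depending on the last observed change) agrees at a 1.0 SD gap: 0.210 / 0.197 = 1.07. At 0.5 SD it gives 0.199 / 0.195 = 1.02.

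Not all of the excess is lost information. In the last row of the table the sampling SD of the estimate is 0.231 planned and 0.221 with interactions, a ratio of 1.045. The rest of the excess is the planned SE overstating its sampling SD (0.238 / 0.231 = 1.03) and the ML SE with interactions understating its own (0.213 / 0.221 = 0.96). REML brings the latter to 0.219 / 0.221 = 0.99.

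Coverage of the planned 95% interval under ML was 95.1% (gap 0.5), 95.7% (gap 1.0) and 96.2% (gap 1.0 with slope 0.5).

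**Bias at month 24.** What matters is the amyloid-positive share among patients still observed. With half of each arm positive at entry:

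- *Dropout 55% in positives and 25% in negatives, both arms:* share 0.45 / (0.45 + 0.75) = 0.375 in each arm; difference 0. Planned and interaction models agree within 0.002 SD. The same holds for equal 40% dropout and for dropout depending on the last observed value.
- *Active 65% / 40%, placebo 40% / 30% (positive / negative):* shares 0.35 / 0.95 = 0.368 and 0.60 / 1.30 = 0.462; difference 0.093. The planned model shifts by 0.024 SD at gap 0.5 and 0.047 SD at gap 1.0.
- *Active 65% / 15%, placebo 40% / 40%:* shares 0.35 / 1.20 = 0.292 and 0.50; difference 0.208. Shifts of 0.057 and 0.11 SD. At gap 1.0 coverage falls to 92.5%.

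The shift is close to half the gap times the share difference (0.5 × 1.0 × 0.093 = 0.047; 0.5 × 1.0 × 0.208 = 0.10). The interaction model removes it.

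**The case against.** The strongest reply is that the plan already deals with amyloid status where it matters. The biomarker and cognition analyses are repeated within each a-PET stratum, and there an omitted `a_PET*Visit` term cannot do harm. That stands. Those analyses still lack `Baseline*Visit`, though, each uses only part of the sample, and the stated objectives concern the overall population, which the pooled model serves.

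Second, a widening gap is plausible but not certain. Protocol 2.7 speaks of progression to dementia, not of change on each scale or biomarker. Protocol 2.3 and 2.7 also cite roughly 70% progression irrespective of amyloid status. No document figure supports the baseline-by-visit effect. This also stands, and it is why the sizes are given as a range that starts at zero.

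Third, the affected analyses are descriptive and unpowered, and the primary test is a t-test on the maximal increment. That is correct and limits the importance of the point.

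A reader might go further and infer that month-24 intervals are too wide as a matter of fact, that the gain from stratification is lost, or that 40% dropout by itself biases the estimate. The documents support none of these. The second simulation's excesses of 15% and 24% need gaps of 1.5 and 2.0 SD, for which there is no basis. Coverage stays near nominal when dropout is alike in the two arms. Bias needs dropout that differs jointly by arm and amyloid status. Nor does the argument reach the antibody-signal MMRM in SAP 6.1.2, because it rests on disease progression.

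**Conclusion.** The point holds for the pooled secondary MMRMs of cognition, PET, CSF and MRI. Their mean model does not allow for the growing amyloid difference that the protocol's own rationale suggests. The cost is modest: a month-24 standard error 0–2% too wide for gaps up to 0.5 SD, 6–7% at 1.0 SD, and about 11% with a strong baseline-by-visit effect as well. Bias of about 0.05–0.11 SD at a 1.0 SD gap, against a standard error of about 0.22, is possible only if the amyloid mix of dropouts differs by arm. Nothing in the documents says that it will, and nothing rules it out.

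All sizes depend on assumed gaps, SDs, correlations and dropout patterns. Only a four-visit schedule was simulated, so the figures carry over to PET, CSF and MRI in direction rather than in size. The primary conclusion is unaffected. This is a cheap improvement to descriptive analyses.

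**What to change.** In SAP 6.1.3 and Protocol 9.1.2.2:

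- Add `Baseline*Visit` and `a_PET*Visit` to the pooled models for cognition, PET, CSF biomarkers and MRI.
- Add only `Baseline*Visit` to the models fitted within one a-PET stratum.
- Leave the antibody-signal MMRM in SAP 6.1.2 as it is.
- Make the change together with a move from ML to REML for these models. In the second simulation the ML fit with interactions rejected a true null in 5.6% of trials at a 1.0 SD gap, against 4.1% as planned.

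The cost is one line of code, matching SAP text and no new data. The pooled models gain 2 × (visits − 1) parameters: six for a four-visit scale, four for MRI, two for PET and CSF. With no true gap, the interactions cost nothing in standard error under ML and about 0.6% under REML.

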9.1.3 Safety Analysis (Part A)

All the safety variables will be evaluated in the Safety population.

9.1.3.1 Primary Safety Analysis

The primary safety variable is the frequency (%) of Adverse Events (AEs). The primary safety endpoint will be analyzed descriptively in the Safety population. For this primary safety analysis, the amyloid-PET negative and the amyloid-PET positive subjects within each treatment group will be pooled together.

The trial will be considered satisfactory if the pattern of AEs (overall or grouped as neurological, psychiatric or cardiovascular) is consistent with a good safety and tolerability profile of ABvac40 for human administration.

All AEs will be coded using the last version of the MedDRA dictionary where neurological AEs corresponds with the System Organ Class (SOC) Nervous system disorders, psychiatric AEs corresponds with the SOC Psychiatric disorders, and cardiovascular SOC corresponds with Vascular Disorders and Cardiac disorders.

The number and percentage of patients in each treatment group reporting at least 1 occurrence of an AE for each unique SOC and PT will be tabulated. AEs will be also tabulated by severity and by the relationship to study medication in each treatment group as assessed by the investigator. Patients who experienced multiple adverse events with the same PT will be counted once for the summaries, using the worst severity. Specific tables will be provided for AEs of special interest such as neurological, psychiatric and cardiovascular AEs.

As an exploratory analysis, the incidence of AEs (overall or grouped as neurological, psychiatric or cardiovascular) will be compared between the group receiving the active treatment (ABvac40) and the control group receiving placebo. Fisher's exact test will be used for these analyses.

9.1.3.2 Secondary Safety Analysis

The safety and tolerability analysis will be based on the safety population, comprising all subjects who took at least one dose of study medication.

Withdrawal criteria (discontinuation decision):

Withdrawal criteria will be summarized using descriptive statistics.

Number of withdrawn patients due to adverse events (AEs); reason for withdrawal:

The number and percentage of patients (in each treatment group) prematurely discontinuing study treatment due to an AE will be tabulated by SOC and PT. Listings of patients with AEs leading to discontinuation and individual narrative summaries for these cases will be provided.

Serious adverse events (SAEs)

The number and percentage of patients in each treatment group reporting at least 1 occurrence of a SAE for each unique SOC and PT will be tabulated. SAEs will be also tabulated by the relationship to study medication in treatment groups as assessed by the investigator. Listings of patients with SAEs (and deaths) and individual narrative summaries for these cases will be provided.

Physical and neurological examination

Physical findings (normal and abnormal) will be listed for each clinical trial subject. Any clinically significant abnormality developed by individual during the clinical trial and not already present at baseline will be reported as an AE.

Physical and neurological examination data will be summarized in tables.

Concomitant medication

Concomitant medication and concomitant therapy will be summarized as number of patients being treated with each type of medication/therapy classified according to ATC level 3 and World Health Organization (WHO) Drug Dictionary preferred term.

Vital signs and anthropometric data

Vital signs (blood pressure, heart rate, respiratory rate and body temperature) and anthropometric data (body mass index, weight and height) will be summarized together with changes from baseline.

Brain MRI

Brain MRI findings will be listed for each clinical trial subject and summarized in tables.

ECG

Overall interpretation of ECG results (i.e. normal or abnormal and clinical significance) as well as ECG findings will be summarized in tables.

Laboratory safety assessments

For laboratory data, summary statistics will be produced for observed values and for changes from baseline to each visit. In addition, the number of abnormal and clinically significant observations will be tabulated for each treatment group by visit. Abnormal values will be flagged in listings.

Shift tables will show the number of patients who changed from below, within or above the reference range at baseline to below, within or above the reference range at each time of assessment.

For laboratory values which are below the limit of quantification, the value corresponding to the limit of quantification will be used when summarizing data (e.g. if the result is <x.xx then the value x.xx will be used in the statistical analysis). “Overflow” readings in OD signal will be replaced by the maximal signal measurable by the Microplate reader.

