4.1 Endpoints

4.1.1 Part A

The primary endpoint for safety is the incidence of AEs (overall or grouped as neurological, psychiatric or cardiovascular).

The hypothesis for the primary endpoint for safety is that ABvac40 will be safe for human administration, according to the observed pattern of AEs. The trial will be considered satisfactory if the pattern of AEs (overall or grouped as neurological, psychiatric or cardiovascular) is consistent with a good safety and tolerability profile of ABvac40 for human administration at the final visit.

Additionally, the following secondary safety endpoints will be evaluated including:

- number of withdrawn patients due to adverse events (AEs)
- number of withdrawn patients due to other causes
- number of serious adverse events (SAEs)
- number of clinically significant changes in physical and neurological examination
- number and type of concomitant medications
- number of clinically significant changes in vital signs (blood pressure, heart rate, respiratory rate, body temperature), body mass (weight, height).
- number of clinically significant changes in brain MRI
- number of clinically significant changes in electrocardiogram (EKG)
- number of clinically significant changes in analytical haematology, biochemistry, coagulation, serology and urine test strip results.

The primary efficacy endpoint is the average maximal increment ($M\Delta$) of anti-A β 40 antibody signal (OD in ELISA) in each subject with regard to the pre-treatment visit (either V0 or V1).

For the primary efficacy analysis, the trial will be considered successfully confirmatory regarding efficacy (immunogenicity) of ABvac40 if the average maximal increment ($M\Delta$) of anti-A β 40 antibody signal (OD in ELISA) in the verum group is >0 OD than the average $M\Delta$ in the placebo group. For the secondary efficacy analysis, the trial will be considered satisfactory if the difference of the average maximal increment ($M\Delta$) of anti-A β 40 antibody signal (OD in ELISA) in the treated group is > 1.778 OD than the average $M\Delta$ in the placebo

group; the difference that was reached between both groups in the phase I clinical trial of ABvac40.

Additionally, the following secondary efficacy endpoints will be evaluated including:

- Characterization of the immune response:
 - o Levels of anti-KLH and anti-A β 42 antibodies in plasma
 - o Level of anti-A β 40 antibodies in CSF

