8.2.6 Brain MRI

The brain MRI in the AB1601 study is fundamentally a safety protocol designed to identify the occurrence of cerebral complications secondary to the administration of ABvac40. It will be performed at visits V0, V9, V16, V17, V21 and V25 during Part A and at visits V1B (only in the absence of a MRI performed within 6 months (± 15 days)), V9B, V16B, V17B, V21B and V22B during Part B, and will be assessed centrally by the MRI Central Reader. Additionally, data from MRI at visits V0, V16, V21, V25, V16B, V21B and V22B will be used for exploratory efficacy analysis (see section 7.2.1). The MRI at the pre-selection visit (V0) will also be used to see if patients who want to enter the study meet the criteria for inclusion and none of the exclusion criteria.

Electronic MRI results will be uploaded to the subject's eCRF. Detailed procedures for acquiring, recording and assessing MRI results are described in the Neuroimaging Management document.

Any new finding or worsening of a previous finding will be recorded in the subject's eCRF as an AE. Particular attention will be paid to the so called Amyloid Imaging Related Abnormalities (ARIA). The spectrum of ARIA includes signal hyperintensities on fluid attenuation inversion recovery sequences thought to represent "vasogenic edema" and/or sulcal effusion (ARIA-E), as well as signal hypointensities on GRE/T2* thought to represent hemosiderin deposits (ARIA-H), including microhemorrhage and superficial siderosis.

A decision tree is set in place for the management of these SAE in case of occurrence (see section 8.3.10).

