- Any new micro-hemorrhage (1 or more) showed in the follow up MRIs and/or Protocol MRIs in a subject with previous ARIA-H will be consider a progression of previous ARIA-H if the patient DID NOT TAKE the study medication in between of MRI examinations. In such cases, a Follow up SAE will be completed with all information

(Follow up SAE will be completed, regardless of new findings, after a Follow Up MRI in order to keep [REDACTED] Drug Safety informed on the progression of patients).

- Any new micro-hemorrhage (1 or more) showed in the follow up MRIs and/or Protocol MRIs will be consider a NEW ARIA-H if the patient took the study medication in between of MRI examinations and in such case, a new SAE Report Form will be completed with all information required.

ARIA Thresholds and ARIA Decision

We propose this to be based in the guidelines published by the Alzheimer Association Research Roundtable Working Group (Sperling et al. 2011) as follow.

1. Patients developing mild ARIA-E or mild ARIA-H (≤ 3 incident micro-haemorrhages) without clinical symptoms could continue in the study.
2. Patients developing moderate or severe ARIA-E (as assessed by the MRI central reader) without clinical symptoms, or those with ARIA-E accompanied by mild clinical symptoms, will suspend treatment and resume once ARIA (and symptoms, if any) resolved.
For these patients, if ARIA appears at the MRI after the third shot and resolve within two months, they resume for the remaining two shots and booster; if ARIA does not resolve within two months then, they resume at the booster shot (m10) if resolved; otherwise, they permanently discontinue treatment.
3. Patients who develop ARIA-E or ARIA-H (≤ 3 incident micro-haemorrhages) accompanied by moderate, severe, or serious clinical symptoms, >3 incident micro-haemorrhages, any incident macro-haemorrhage, or >1 incident haemosiderosis at any time during the study will permanently discontinue treatment.

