4 STUDY VARIABLES

4.1 Safety Variables (Part A and Part B)

4.1.1 Primary Safety Variable – Adverse Events

AEs experienced by the patients will be collected throughout the entire study and will be coded using version 20.0 of the Medical Dictionary for Regulatory Activities (MedDRA). Serious AEs of special interest (SAESIs) will be defined as:

- Amyloid Related Imaging Abnormalities (ARIA), either
 - ARIA-micro-hemorrhage (ARIA-H), or
 - ARIA-vasogenic edema and/or sulcal effusion (ARIA-E)

- Aseptic Meningo-Encephalo-Myelitis

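### The SAP omits the brain MRI safety summary promised in the protocol, leaving ARIA to adverse event tables, and words ARIA-H more narrowly than the protocol does

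*Protocol*

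**What the plan says.** **Protocol.** Section 4.1.1 lists among the secondary safety endpoints the "number of clinically significant changes in brain MRI". Section 8.1 repeats brain MRI as a secondary safety variable. Section 8.2.6 states the purpose: "The brain MRI in the AB1601 study is fundamentally a safety protocol designed to identify the occurrence of cerebral complications". Section 9.1.3.2 commits to the output: "Brain MRI findings will be listed for each clinical trial subject and summarized in tables". Section 8.2.6 describes ARIA-H as hemosiderin deposits, "including microhemorrhage and superficial siderosis". It also makes MRI findings adverse events: "Any new finding or worsening of a previous finding will be recorded in the" eCRF as an AE. Section 8.3.10.1 then decides how a further micro-haemorrhage is filed in a patient who already has ARIA-H. It is progression of the earlier event "if the patient DID NOT TAKE the study medication in between of MRI examinations", and a new ARIA-H with a new SAE form if a dose was taken between the scans.

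**SAP.** Section 4.1.2 lists withdrawal criteria, physical and neurological examination, concomitant medication, vital signs, ECG and laboratory tests as secondary safety variables. Section 7.3 gives a subsection to each. Brain MRI is in neither place. It appears only as volumetry among the disease biomarkers (Section 4.2.2.2) and as a condition for entering Part B (Section 2.3). Section 9.2, the list of changes from the protocol, does not mention it. Section 4.1.1 defines the serious adverse events of special interest (SAESIs) and words the haemorrhagic kind of ARIA as "ARIA-micro-hemorrhage (ARIA-H), or"; the abbreviation list agrees. Where analyses differ between the documents, "those found in this SAP will assume primacy".

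**The concern.** ARIA is the safety question specific to an anti-amyloid vaccine, and it is found by scanning. With no MRI section in the SAP, the final report is planned to describe ARIA only through adverse event records. That leaves three questions without a planned answer by arm:

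- of the patients scanned at each MRI visit, how many had a new lesion;
- how many had accumulated more than 3 new micro-haemorrhages against V0, the threshold the protocol itself uses;
- how lesions progressed in patients who already had ARIA-H.

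Baseline matters here because exclusion criterion 14 allows entry with up to 3 micro-haemorrhages.

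The narrower ARIA-H wording adds a second problem. An event outside the SAESI definition loses its place in the special-interest table and is assigned to a treatment group under a different rule.

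**Working it through.** The plan gives no figure on which this point turns, so there is none to reproduce. The check compares the texts and counts intervals.

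**Step 1. What the adverse event tables can show.** SAP 7.2.1 gives counts and percentages of patients by treatment group, SOC and PT. The denominator is every patient who took at least one dose of the product concerned. There is no number scanned, no lesion count and no comparison with V0.

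**Step 2. Where later lesions are filed as follow-up.** Inputs are the Part A MRI visits (Protocol 8.2) and dose visits (Protocol 4.4.1, Table 6), with weeks from the schedule of procedures.

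| MRI interval | Weeks | Doses in between (week) | New micro-haemorrhage after earlier ARIA-H |
|---|---|---|---|
| V0 to V9 | -8 to 10 | 0, 4, 8 | new event |
| V9 to V16 | 10 to 24 | 12, 16 | new event |
| V16 to V17 | 24 to 40 | none | follow-up of earlier SAE |
| V17 to V21 | 40 to 50 | 42 | new event |
| V21 to V25 | 50 to 104 | none | follow-up of earlier SAE |

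So 2 of 5 intervals are dose-free for a fully dosed patient followed to V25. Part B gives the same count, 2 of 5: V16B to V17B (weeks 24 to 40) and V21B to V22B (weeks 50 to 77). The follow-up branch also applies to an unscheduled scan with no dose since the previous MRI, and to every later scan in a patient who has stopped treatment.

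**Step 3. Effect on the patient count.** The follow-up branch needs an earlier ARIA-H. That patient is already counted once, so within a treatment group the number with any ARIA-H does not change. What is lost is the later lesion, its date and the cumulative total.

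**Step 4. Effect of the narrower ARIA-H wording.** Take a patient randomised to ABvac40 in Part A whose superficial siderosis is first seen at the scheduled V9B scan, with onset dated to that scan.

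- Part B placebo injections before that scan: weeks 0, 4 and 8 (V1B, V4B, V7B).
- ABvac40 booster: week 16 (V13B).
- V9B MRI: week 10, so the last injection before onset is the week 8 placebo.
- Under the SAESI rule in SAP 7.2.1, an event at any time after the first ABvac40 dose belongs to ABvac40.
- Under the non-SAESI rule, an event before the booster belongs to the last injection received, so this one belongs to Placebo.

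The same finding in the same patient changes column according to whether siderosis is read as part of ARIA-H.

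**The case against.** Much can be said on the other side, and several stronger readings fail.

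- **Later lesions are always absorbed into earlier events.** A reader might infer this from the follow-up rule. The documents do not support it: the rule needs an earlier ARIA-H and no dose between scans, and 3 of 5 scheduled intervals fall on the new-event side. It governs SAE forms, while Protocol 8.2.6 separately requires any new or worsened finding to be recorded as an AE.
- **Counts of patients with ARIA-H are too low.** Step 3 shows otherwise within a group. A shift between groups is conceivable for a delayed-start patient with ARIA-H under placebo and a further lesion in a dose-free Part B interval, but Part B entry requires no MRI safety issues (Protocol 2.6), which limits this.
- **The dose-free time measures the harm.** The two intervals cover (40 - 24) + (104 - 50) = 70 of 104 weeks, or 67%. This is calendar time, not patients or events. It concerns a subset of unknown size and assumes follow-up to V25, whereas patients may enter Part B after V23.
- **Siderosis disappears.** It does not. It remains an AE, appears in the general tables, and appears in the serious-event tables if reported as serious. The SAP phrase may be a gloss and not an exclusion, and the reporting rule in Protocol 8.3.10.1 is itself written around micro-haemorrhage.
- **Patients with more than 3 new lesions cannot be seen at all.** Those who stop treatment for this should surface among events leading to discontinuation and in the individual listings. Cases arising after the last dose might not.
- **MRI alone was left out.** The weight and BMI changes from baseline promised in Protocol 9.1.3.2 are also absent from SAP 4.1.2 and 7.3.5.

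Finally, the SAP says it supplements the protocol, and its table and listing specifications are in separate documents, so an MRI output may exist there. The interim monitoring package does include safety MRI (Protocol 9.1.5.1). These points stand as cautions. They do not supply the missing section: the SAP describes itself as a rewritten stand-alone document, its change list is silent, and the two scheduled interim reviews are tied to the 24-week visit or October 2020, not to the final data.

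**Conclusion.** The concern holds in this form. The SAP leaves out a safety summary that the protocol promises, does not say so, and takes precedence. The planned final reporting of ARIA therefore rests on adverse event tables and listings, whose tables carry no lesion counts, no accumulation against V0 and no scanned denominators.

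The loss is one of information on burden, timing and progression. No bias in the number of patients with ARIA-H within a group is shown. The follow-up rule contributes in 2 of 5 scheduled intervals in each part, assuming full dosing and, in Part A, follow-up to V25.

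The ARIA-H wording is a smaller, separate matter. It can move a siderosis event from ABvac40 to Placebo in an ABvac40-first patient when onset falls after a Part B placebo injection and before the booster. This assumes that siderosis is treated as outside the SAESI definition. The documents give no ARIA or siderosis rate for this trial from which to say how often that would occur.

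The conclusion on the omission rests on the SAP text; the separate output specifications were not available. The point should be corrected before the final analysis, but it does not threaten the primary immunogenicity result.

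**What to change.** 1. Restore brain MRI to SAP 4.1.2 and add a subsection to SAP 7.3 based on the central reads. It should contain a subject listing and one table by arm and scheduled MRI visit, with the number scanned shown. The table should give patients with new ARIA-E, new micro-haemorrhage since V0 (cumulative count, including more than 3), new superficial siderosis and macro-haemorrhage. The listing and summary table are what the protocol already promises; the scanned denominators and cumulative bands go further, and are recommended because they answer the questions the AE tables cannot.
2. Align the ARIA-H definition in SAP 4.1.1 and the abbreviation list with Protocol 8.2.6, so that siderosis enters the SAESI table and its attribution rule.
3. If any omission is intended, state and justify it in SAP 9.2.

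The cost is one SAP subsection, one table and one listing from data already collected. No change to any dosing or stopping rule is proposed.
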